**Rating Scale using interactive voice response technology. J Psychiat Res. 2010; 44(16):1224-1228.**

33. Update Abbreviations table to include protocol changes.

Section 12 Appendices, Section 12.1 Appendix 1: Abbreviations and Trademarks

CRP	C-reactive Protein
C-SSRS	Columbia-Suicide Severity Rating Scale
CTA	Computed Tomography Angiography
CV	Cardiovascular
DBL	Database lock
dL	Deciliter

Administrative changes

Updated author list and Table of Contents

GSK	GlaxoSmithKline
HAQ-DI	Health Assessment Questionnaire – Disability Index
ICH E9	International Council for Harmonization Efficacy guideline 9
IDMC	Independent Data Monitoring Committee
IFN	Interferon
IL	Interleukin
IP	Investigational Product
ITT	Intent-to-Treat
MACE	Major Adverse Cardiac Events

MCS	Mental Component Summary
MedDRA	Medical Dictionary for Regulatory Activities
MMRM	Mixed Model for Repeated Measures
NRS	Numeric Rating Scale
P1NP	Procollagen Type 1 N-propeptide
PCI	Potential Clinical Importance
PCS	Physical Component Summary
PD	Pharmacodynamics
PGIC	Patient Global Impression of Change
PH	Proportional Hazards
PK	Pharmacokinetics
PMR	Polymyalgia Rheumatica
PP	Per Protocol
PT	Preferred Term
PhGA	Physician Global Assessment of disease activity
PtGA	Patient Global Assessment of disease activity
PRO	Patient-Reported Outcomes
q2w	Every 2 weeks
q4w	Every 4 weeks
SAE	Serious Adverse Event
SAP	Statistical Analysis Plan
SAS	Statistical Analysis System
SC	Subcutaneous
SD	Standard Deviation
SE	Standard Error
SIQ	Steroid Impact Questionnaire
SF-36v2	36-item Short Form health survey version 2
SMQ	Standardized MedDRA Query
SOC	System Organ Class
TEAE	Treatment-Emergent Adverse Event
TEAESI	Treatment-Emergent Adverse Event of Special Interest

US	Ultrasound
VAS	Visual Analogue Scale

1. Introduction

Sirukumab is a human anti-interleukin (IL)-6 immunoglobulin G1 (IgG1) kappa monoclonal antibody with a high affinity and specificity for binding to the human IL-6 molecule that is being developed for the treatment of giant cell arteritis (GCA).

Multiple lines of evidence support a role for IL-6 in the pathophysiology of GCA. Sirukumab may have therapeutic benefit in the treatment of GCA by interruption of multiple pathogenic pathways. The purpose of this study is to evaluate the efficacy and safety of sirukumab to characterize the benefit-to-risk profile of sirukumab in the treatment of active GCA.

This Statistical Analysis Plan (SAP) is based on the protocol version 3.0 dated of 17th November 2016. This SAP contains definitions of analysis sets, derived variables and statistical methods for the analyses of efficacy and safety endpoints.

[Section 4](#) to [Section 10](#) focus on Part A of this study. Specific derivations for Part B will be presented in [Section 11](#).

1.1. Changes in the Planned Analysis due to Study Termination

This SAP reflects the analyses done given study termination, and are not aligned with planned analyses as per protocol.

Due to the sponsor's decision to terminate the study, data for the following endpoints/objectives are not available. Therefore, the following objectives will not be reported in this planned analysis:

- Pharmacokinetic objectives
- Immunogenicity objectives
- Pharmacodynamic objectives
- Pharmacogenetics objectives
- Vascular ultrasound objectives

Additionally:

- Available data for exploratory objectives / endpoints related to biomarkers will only be listed.
- No statistical analysis will be carried out for efficacy objectives / endpoints due to the limited number of subjects completing the study at week 52.
- However, [Section 2.1](#) and [Section 3.2](#) list respectively objectives and endpoints as specified in the protocol.
- Protocol endpoint "Median and cumulative prednisone dose over time" is modified to "Cumulative prednisone dose over time" as median prednisone dose will be provided as part of the summary statistics for cumulative prednisone dose.
- Protocol wording "GCA flare" is modified to "disease flare" for consistency across endpoints in this document.

Due to study termination on 10th October 2017, early withdrawal visits were completed for all subjects by 30th November 2017. All subjects are required to have a safety follow-up visit 16 weeks (+/- 1 week) after the early withdrawal visit. The study should be terminated for an individual subject after they have completed the 16-week safety follow-up visit, unless there is a need for additional post-study visits for continued evaluation of an ongoing adverse event. However, if an anti-IL6, any biologic or investigational agent is initiated, the subject will be withdrawn from the 16-week safety follow up.

To facilitate patient management, treatment codes for the blinded prednisone study drug will be broken and provided to the investigator at the Early Withdrawal Visit, when occurring after sponsor's decision to terminate the study. Treatment codes for the subcutaneous investigational product (sirukumab or placebo) will be unblinded at the end of the study, after database lock. However, unblinding for the subcutaneous investigational product can be requested for individual subjects at any time for safety management. In addition, CRP value from the Early Withdrawal Visit will be provided to the investigator to facilitate subject management.

2. Objectives

Due to the sponsor's decision to terminate the study and the data not being available, the endpoints for the following objectives will not be reported in this planned analysis:

- Pharmacokinetic objectives
- Immunogenicity objectives
- Pharmacodynamic objectives
- Pharmacogenetics objectives
- Vascular ultrasound objectives: Even though 3 subjects were randomized to the US imaging portion of the study, only one patient passed the Week 12 visit. There was no sufficient data collected to perform any analysis, so no data for this cohort of subjects will be reported.

The pharmacokinetic, immunogenicity, pharmacodynamic (IL-6) and pharmacogenetics samples will not be analyzed, therefore there will be no data related to these endpoints and these objectives that can be reported.

However, [Section 2.1](#) and [Section 2.2](#) lists objectives as specified in the protocol.

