## **4.2. Treatment Arms and Duration**

### **4.2.1. Part A: 52-week double-blind treatment phase**

Following the Screening period, eligible subjects will be randomized at Baseline into Part A in a ratio of 3:3:2:2:2 to one of five treatment arms:

1. Treatment Arm A: Sirukumab 100 mg SC q2w for 52 weeks plus a pre-specified maximum of 6-month prednisone taper regimen(n=51)
2. Treatment Arm B: Sirukumab 100 mg SC q2w for 52 weeks plus a pre-specified maximum of 3-month prednisone taper regimen (n=51)
3. Treatment Arm C: Sirukumab 50 mg SC q4w for 52-weeks plus a pre-specified maximum of 6-month prednisone taper regimen (n=34)
4. Treatment Arm D: Placebo SC q2w for 52 weeks plus a pre-specified maximum of 6-month prednisone taper regimen (n=34)
5. Treatment Arm E: Placebo SC q2w for 52 weeks plus a pre-specified maximum of 12-month prednisone taper regimen (n=34).

All subjects must be receiving prednisone (a minimum dose of 20 mg/day) at the start of Screening. Prednisone treatment must be initiated at Screening for subjects not currently receiving steroid treatment. The prednisone tapering schedule (summarized in Section 6.3) will be initiated at randomization for all subjects. Subjects should remain on the prednisone dose they are currently receiving at Baseline (randomization) for one week. At Week 1, the prednisone dose should be decreased in accordance with the pre-specified prednisone taper schedule. The pre-specified maximum tapering schedule to be followed will depend on the subject's treatment group assignment. The standardized prednisone taper regimen will be unblinded (open-label) with identical weekly decreases in dose according to the starting dose for all subjects, until subjects reach a dose of 20 mg/day. Thereafter, prednisone dosing will be blinded to allow for the pre-specified differences in duration of the prednisone tapering. Subjects who are receiving a prednisone dose of open-label 20 mg/day at randomization should continue taking the 20 mg daily dose for one week. At Week 1, these subjects will initiate the blinded taper regimen.

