### 4.3. Type and Number of Subjects

Approximately 204 subjects with a diagnosis of GCA based on the Revised GCA Diagnosis Criteria will be randomized at Baseline into the 52-week double-blind, placebo controlled phase (Part A) of the study. Eligible subjects will include both GCA patients with new onset disease (diagnosis within 6 weeks of baseline) and relapsing/refractory (established diagnosis greater than 6 weeks prior to baseline with disease activity within 6 weeks of baseline). Relapsing/refractory subjects include those who may have previously been in remission with corticosteroid treatment and have recurrence of disease activity (relapsing) or subjects who continued to have active disease without remission despite previous or ongoing corticosteroid therapy.

The number of relapsing/refractory subjects will be capped at approximately 50% to ensure that a sufficient number of subjects with new onset disease are recruited.

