3.3. Treatments

Two doses of sirukumab (100 mg subcutaneous [SC] q2w and 50 mg SC q4w) were selected based on doses which have demonstrated efficacy in a Phase II study of rheumatoid arthritis subjects and are presently under investigation in Phase III studies for the treatment of moderate to severe rheumatoid arthritis. The 100 mg SC q2w dose of sirukumab has shown numerical superiority at 24 weeks in some efficacy endpoints (American College of Rheumatology criterion ACR20, change in disease activity score) over other sirukumab doses tested in the Phase II study and may be more likely to provide a clinically meaningful response in an IL-6– mediated disease such as GCA. The 50 mg q4w dose of sirukumab will also be evaluated to more fully characterize the benefit-to-risk profile of sirukumab in GCA.

Following the screening period, eligible subjects will be randomized to receive sirukumab (100 mg SC q2w or 50 mg SC q4w) or matching placebo. All subjects will receive prednisone during the 52-week double-blind treatment period according to a pre-specified taper regimen.

Table 1 Investigational Product and Other Study Treatment

Product name	Study Treatment		
	Sirukumab	Placebo	Prednisone/ prednisone placebo
Dosage form	1.0 mL prefilled syringe	1.0 mL prefilled syringe	Tablets
Unit dose strength(s) / dose level(s)	100 mg/mL or 50 mg/mL	--	Up to-60 mg/day
Route of administration	SC	SC	Oral
Dosing instructions	SC q2w (treatment arms A & B) SC q4w (treatment arm C)	SC q2w (treatment arms D & E)	20-60 mg/day open-label, then 0-18 mg/day taper (blinded)

SC=subcutaneous; q2w=every 2 weeks; q4w=every 4 weeks.

Note subjects randomized to treatment arm C will alternate between sirukumab 50 mg SC and matching placebo SC injections in order to maintain the blind.

In Part A, eligible subjects will be randomized in a ratio of 3:3:2:2:2 to one of the 5 treatment arms described in [Table 2](#). The treatment descriptors and column headings in [Table 2](#) will be used in all data displays.

Table 2 Treatment Descriptors and Column Headings for Part A

Treatment Group	Treatment Descriptor	Column Header
Arm A	Sirukumab 100 mg SC q2w for 52 weeks plus a prespecified maximum of 6-month prednisone taper regimen	Sirukumab 100mg SC q2w + 6 month prednisone
Arm B	Sirukumab 100 mg SC q2w for 52 weeks plus a prespecified maximum of 3-month prednisone taper regimen	Sirukumab 100mg SC q2w + 3 month prednisone

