Investigators and the sponsor/study team will remain blinded to the results of the fasting lipids, CRP and ESR laboratory tests after the start of treatment. Investigators and the study team will have access to Screening and Baseline values, and will thereafter remain blinded to these results until the end of Part A. Alerts will be provided by the central laboratory for abnormal, clinically significant findings to enable investigators to manage subject safety. Since the ESR is measured at the site, an unblinded assessor at the local laboratory will report the ESR results. The investigator will be notified of the value of the ESR result when an ESR result is >40 mm/hr in order to determine if a treatment change is warranted. Investigators are advised to consider these notifications of an elevated ESR which has reached the alert value as an additional element in the determination of whether a subject is experiencing GCA disease flare. An elevated ESR in isolation should not be the sole basis for investigator assessment of disease flare, particularly in the absence of clinical symptoms (e.g. cranial or polymyalgia rheumatic [PMR]) suggestive of disease activity.

Due to the sponsor's decision to terminate the study, to facilitate patient management, treatment codes for the blinded prednisone study drug will be broken and provided to the investigator at the Early Withdrawal Visit, when occurring after sponsor's decision to terminate the study. Treatment codes for the subcutaneous investigational product (sirukumab or placebo) will be unblinded at the end of the study, after database lock. However, unblinding for the subcutaneous investigational product can be requested for individual subjects at any time for safety management. In addition, CRP value from the Early Withdrawal Visit will be provided to the investigator to facilitate subject management.

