9.1.8. Adverse Events of Special Interest

The identification, classification and adjudication of adverse events of special interest (AESI) will occur in a blinded fashion quarterly by the GSK medical monitor. The final adjudication will take place prior to database releases and will be performed for reporting purposes.

Where available, AEs will have SMQ flags assigned to help the adjudication process at GSK. These flags will help but not over-rule individual event adjudication performed by GSK. All AE terms will be adjudicated at the subject level by GSK, in order to identify any events that are AESI as defined by the protocol as well as to assign each AESI category which will support later tabulation.

The groups of adverse events of special interest are defined below:

- Gastrointestinal perforation
- Diverticulitis
- Tuberculosis activation
- Serious/opportunistic infections

- Hypersensitivity
- Cytopenias
- Serious cardiovascular events
 - Major Adverse Cardiac Events (MACE) adjudicated by the CEC
 - MACE
- Malignancies
- Injection site reactions
- Severe flares including hospitalizations
 - Total/partial blindness
 - Limb claudication
 - Scalp or tongue necrosis
- Lipid increases
- Liver function test abnormalities
- Corticosteroid-related AE

An overall summary of AESIs will be presented summarizing numbers and percentages of subjects with events within each of the above categories as well as by SOC and PT.

Further details will be provided in summaries of each AESI separately. The summary of event characteristics will also be provided, including number of subjects with at least one event, number of events, the event characteristics (i.e. seriousness, relationship to study drug, severity and if the event was fatal or not), the number of occurrences, the outcome, the maximum intensity and the action taken. The worst case approach will be applied at subject level for the event outcome and the action taken, (i.e. a subject will only be counted once as the worst case from all of the events that that subject had). In addition, onset and duration of the first occurrences for each type of events will be summarized.

Time to onset of first AESI will be displayed and calculated as:

$$\text{Date of onset of first AESI} - \text{Date of first SC IP date} + 1 \text{ day}$$

Duration of first AESI will be displayed and calculated as:

$$\text{End date of first AESI} - \text{Start date of first AESI} + 1 \text{ day}$$

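### The prednisone code released at Early Withdrawal visits also identifies the injected product in Arms B and E, so the SAP's statement that it stays blinded to database lock is wrong for those arms

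*SAP*

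**What the plan says.** SAP 1.1 describes conduct after the termination decision. To help investigators manage their patients, "treatment codes for the blinded prednisone study drug will be broken and provided to the investigator at the Early Withdrawal Visit". For the injections it says: "Treatment codes for the subcutaneous investigational product (sirukumab or placebo) will be unblinded at the end of the study, after database lock". The only stated exception is unblinding of individual subjects on request for safety reasons. SAP 4.2 repeats the arrangement ("treatment codes for the blinded prednisone study drug will be broken and provided to the investigator") and the same promise about the injections.

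A safety follow-up visit comes 16 weeks (plus or minus one) after the Early Withdrawal visit. Under SAP 9.1, events in early withdrawals count as treatment-emergent until 16 weeks after the final injection. SAP 9.1.2 takes relatedness from the investigator and splits it between SC product and prednisone. SAP 9.1.3 tabulates severity, which Protocol Appendix 4 assigns to the investigator. SAP 9.1.1 and 9.1.8 give relative risks for six treatment comparisons. SAP 5.1 plans a listing of subjects whose blind was broken.

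**The concern.** The two blinding statements are compatible only if the taper says nothing about the injection. In this design it does: two of the three tapers each belong to a single arm, one active and one placebo. From the code break onward, an investigator with an Arm B or Arm E subject can read the SC product from the arm table. Neither SAP section acknowledges this, and the safety tables treat events before and after the break alike.

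At stake is the reading of the safety results. Efficacy is reduced to summary statistics, so safety is the main comparative output. Whether an event is attributed to the injection or to prednisone is the kind of judgement that knowing both products can shift. A report following the SAP as written would describe these ratings as blind to SC product when, for two of five arms, they need not have been.

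**Working it through.** **Inputs.** Allocation, SAP 3.3: "eligible subjects will be randomized in a ratio of 3:3:2:2:2 to one of the 5 treatment arms". Total, Protocol 4.3: "Approximately 204 subjects with a diagnosis of GCA based on the Revised GCA Diagnosis Criteria will be randomized at Baseline". Arm definitions, Protocol 4.2.1, for example "Treatment Arm B: Sirukumab 100 mg SC q2w for 52 weeks plus a pre-specified maximum of 3-month prednisone taper regimen (n=51").

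**Step 1: reproduce the plan's arm sizes.** Arm size = 204 × ratio / 12. Arms A and B: 204 × 3/12 = 51 each. Arms C, D and E: 204 × 2/12 = 34 each. This matches Protocol 4.2.1 exactly.

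**Step 2: cross-tabulate SC product by taper.**

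| Taper | Arms | Sirukumab | Placebo | Share on sirukumab |
|---|---|---|---|---|
| 3 months | B | 51 | 0 | 100% |
| 6 months | A, C, D | 51 + 34 = 85 | 34 | 85/119 = 71.4% |
| 12 months | E | 0 | 34 | 0% |
| All | | 136 | 68 | 136/204 = 66.7% |

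A 3-month or 12-month code settles the SC product. A 6-month code moves the probability of sirukumab only from 66.7% to 71.4% and reveals nothing definite.

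**Step 3: size.** (51 + 34)/204 = 85/204 = 41.7% of planned subjects. That is 51/136 = 37.5% of planned sirukumab subjects and 34/68 = 50% of planned placebo subjects.

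**Step 4: range for the actual share.** SAP 4.1 gives no actual sample size. Assume that m subjects had the code released and that they follow the planned 5/12 share. The approximate 95% range is then 5/12 ± 1.96 × √(5/12 × 7/12 / m): about 28% to 55% for m = 50, and 32% to 51% for m = 100.

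**Step 5: comparisons touched.** SAP 2.1.1 and 2.1.2 define six contrasts. Four include Arm B or E: B vs D, A vs E, B vs E and C vs E. Two do not: A vs D and C vs D.

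**Step 6: time touched.** If the last injection was d days before the Early Withdrawal visit, the treatment-emergent time after the code break is 112 − d days. With d = 0 this is 16 weeks. The documents give no date on which injections stopped. If it was the termination date (10 October 2017) and the visit fell on the last date stated (30 November 2017), then d = 51 and 112 − 51 = 61 days, or 8.7 weeks. Later events fall in the separate table of post-treatment events.

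**The case against.** The strongest reply is that the SAP is open about the code break, its timing and its reason. It allows individual SC unblinding, plans a listing of broken blinds, and tests no efficacy hypothesis. The primary contrast, A vs D, lies wholly within the 6-month taper. On this view one sentence of disclosure is enough.

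Much of that stands, and it limits the point. Several stronger readings that a reader might infer are not supported:

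- *Adjudication of adverse events of special interest is broken.* SAP 9.1.8 says "The identification, classification and adjudication of adverse events of special interest (AESI) will occur in a blinded fashion" and assigns the work to the sponsor's medical monitor. SAP 1.1 and 4.2 give the prednisone code only to the investigator.
- *Flare follow-up is compromised.* The Follow-up column of the Part A schedule (SAP Table 10) has no disease-activity, global, ESR or CRP assessment.
- *Most subjects are affected.* No figure supports this. The break applies only to Early Withdrawal visits after the termination decision, and their number is not given.
- *Arms A, C and D are unblinded too.* The taper does not do this. The same paragraph releases the Early Withdrawal CRP, which might hint at the SC product, but a hint does not identify it.

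The reply fails on two counts. The individual-request exception does not cover a systematic release that identifies two whole arms. The planned listing neither says that the SC product was revealed nor separates events by timing.

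**Conclusion.** The blinding statement in SAP 1.1 and 4.2 is wrong for Arms B and E from the code break onward. This follows directly from the arm table and needs no assumption. By plan it concerns 41.7% of subjects; the actual count is unknown.

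The consequence is narrower: investigator ratings of relatedness and severity for events after the break in those arms are potentially open. The documents do not show that any rating was changed. Sixteen weeks is a ceiling on the treatment-emergent time involved, reached only if the last injection coincided with the visit. Four of the six relative-risk comparisons include an affected arm; A vs D and C vs D are unaffected by this route. For subjects already in Part B, the code reveals only what they were injected with in Part A.

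This warrants a correction and a sensitivity display. It does not invalidate the safety analysis.

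**What to change.** 1. In SAP 1.1 and 4.2, state that investigators are effectively unblinded to SC product in Arms B and E from the date the prednisone code is released.
2. Flag every adverse event by onset before, or on or after, that date, using the Early Withdrawal visit date. Subjects who withdrew before the termination decision have no code break, so all their events count as before it.
3. Repeat the key treatment-emergent, special-interest and relatedness tables on events before the break. Do the same for the relative risks for B vs D, A vs E, B vs E and C vs E. Apply the cut-off to both arms of each comparison, and end exposure time there in any rate that is repeated.

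The cost is one derived flag and a few extra tables. Release of the code for patient management is untouched. Measures that would have had to be taken at the visits themselves are not proposed, because SAP 1.1 reports that all Early Withdrawal visits were complete by 30 November 2017.
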